#### **7.10.3 Visit 3- Week 4 (Allowed visit window is $\pm$ 5 days)**

1. Evaluate treatment and protocol compliance and record any deviations. This includes a review of the diary card for number of applications and missed applications.
2. Investigator is to document the number and location of the lesions within the treatment area on a grid foil. One copy of the grid foil should be inserted into the subject's source document and the other should be given to the subject for use at home.
3. Collect vital signs (blood pressure and pulse rate).
4. Perform a 12-lead EKG.

5. Collect blood (2/3 tablespoon) and urine for hematology/chemistry/urinalysis safety labs.
6. Conduct a urine pregnancy test for all females of child bearing potential.
7. Collect AE data. This includes a review of the diary card for potential AEs.
8. Update concomitant medications data.
9. Dispense diary and review instructions. Remind subject to bring all tubes of study product to each visit.
10. If subject requires more study product, weigh and then dispense study product as needed from IWRS assignment and collect empty or nearly empty tubes. Weigh tubes when they are collected and prior to re-dispensing. Re-dispense partially filled tubes.
11. Schedule next visit.
12. Complete eCRF.

#### **7.10.4 Visit 4 – Week 8 (Allowed visit window is $\pm$ 5 days)**

1. Evaluate treatment and protocol compliance and record any deviations. This includes a review of the diary card for number of applications and missed applications.
2. Investigator is to document the number and location of the lesions with in the treatment area and on a grid foil. One copy of the grid foil should be inserted into the subject's source document and the other should be given to the subject for use at home.
3. Collect vital signs (blood pressure and pulse rate).
4. Conduct a urine pregnancy test for all females of child bearing potential.
5. Collect AE data. This includes a review of the diary card for potential AEs.
6. Update concomitant medications data.
7. Dispense diary and review instructions. Remind subject to bring all tubes of study product to each visit.
8. If subject requires more study product, weigh and then dispense study product as needed from IWRS assignment and collect empty or nearly empty tubes. Weigh tubes when they are collected and prior to re-dispensing. Re-dispense partially filled tubes.
9. Schedule next visit.
10. Complete eCRF.

#### **7.10.5 Visit 5 – Week 12/End of Treatment Visit (Allowed visit window is $\pm$ 5 days)**

1. Evaluate treatment and protocol compliance and record any deviations. This includes a review of the diary card for number of applications and missed applications.
2. Investigator is to document the number and location of the lesions with in the treatment area and on a grid foil. One copy of the grid foil should be inserted into the subject's source document.
3. Collect vital signs (blood pressure and pulse rate).
4. Perform a physical examination (HEENT, lungs, heart, abdomen, skin, and neurologic).
5. Perform a 12-lead EKG.
6. Collect blood (2/3 tablespoon) and urine for hematology/chemistry/urinalysis safety labs.
7. Conduct a urine pregnancy test for all females of child bearing potential.
8. Collect AE data. This includes a review of the diary card for potential AEs.
9. Update concomitant medications data.
10. Dispense diary and review instructions. Advise subjects that if they still have unreturned tubes of study product, they are not to use any of the study products after this visit.

11. Weigh tubes when they are collected.
12. Schedule next visit.
13. Complete eCRF.

#### **7.10.6 Visit 6 – Week 16/End of Study Visit (Allowed visit window is $\pm$ 5 days)**

1. Evaluate protocol compliance and record any deviations.
2. Investigator is to document the size and location of the lesions with in the treatment area and on a grid foil. One copy of the grid foil should be inserted into the subject's source document.
3. Collect vital signs (blood pressure and pulse rate).
4. Conduct a urine pregnancy test for all females of child bearing potential.
5. Collect AE data. This includes a review of the diary card for potential AEs.
6. Complete eCRF.

#### **7.10.7 Early Withdrawal**

If a subject is withdrawn from the study according to any of the criteria defined in Section 7.6, the following procedures will be performed:

1. Evaluate treatment and protocol compliance and record any deviations. This includes a review of the diary card for number of applications and missed applications.
2. Investigator is to document the number and location of the lesions with in the treatment area and on a grid foil. One copy of the grid foil should be inserted into the subject's source document.
3. Collect vital signs (blood pressure and pulse rate).
4. Perform a physical examination (HEENT, lungs, heart, abdomen, skin, and neurologic).
5. Perform a 12-lead EKG.
6. Collect blood (2/3 tablespoon) and urine for hematology/chemistry/urinalysis safety labs.
7. Conduct a urine pregnancy test for all females of child bearing potential.
8. Collect AE data. This includes a review of the diary card for potential AEs.
9. Update concomitant medications data.
10. Weigh tubes when they are collected.
11. Complete eCRF.

## **8 ADVERSE EVENTS**

Adverse Events will be documented at Visits 2 to 6. The definitions as laid down in GCP-V § 3 (6) – (9) will be the basis for the safety assessments in this clinical study.

Adverse events will be collected by spontaneous reports from subjects, either verbal or recorded in the subject diary, by directed questioning of subjects, and by observation.

Baseline assessments are made prior to first application. For medical conditions present at Baseline, an adverse event should be recorded at subsequent visits if the severity is worse than Baseline.

---

An adverse event is any untoward medical occurrence in a subject participating in a clinical trial. The event does not necessarily have to have a causal relationship with the study product. An adverse event can therefore be any sign, symptom, or disease, or any worsening of an existing sign, symptom, or disease, whether or not considered related to the study product or trial procedures, including injuries.

Any medical condition that is present at the time of Screening or Baseline should be considered as medical history and reported on the medical history CRF and should not be reported as an adverse event except for adverse events observed at the Baseline Visit due to study procedures performed at the Screening Visit which should be reported. Anticipated day-to-day fluctuations of pre-existing conditions should not be reported as adverse events. Unexpected worsening of pre-existing conditions should be reported as adverse events. The disease or condition being studied or expected progression, signs, or symptoms of the disease or condition being studied should not be reported as an adverse event unless more severe than expected.

All serious adverse events, all study-product-related adverse events and all adverse events leading to study product discontinuation must be followed until the clinical outcome is determined or until all attempts to determine resolution of the event are exhausted (“not recovered” is not an acceptable outcome for acute conditions). For other adverse events, the status at the last visit can be entered into the CRF.

### **8.1 Adverse Event Reporting Period**

Adverse event data must be collected from the time treatment is initiated until the Week 16/End of Study Visit takes place. Adverse events occurring from the time of the Screening Visit until the Baseline Visit associated with study procedures should also be reported for all subjects including screen failures.

### **8.2 Recording Adverse Events**

All AEs will be documented including

- Severity (see [8.3.1: Severity](#) for details)
- Start and stop date
- Causality assessment with study medication
- Measures / action taken
- Serious AE (yes/no)

All AEs will be followed-up until resolution or the End of Study Visit and documented in CRF and subject's medical file.

SAEs will be documented in the subject's medical file, the CRF and on the SAE-form. A copy of the SAE form will be emailed or faxed to the Sponsor and filed in the Investigator's File.

Local Reactions in the treatment area will be documented separately. The following local reactions will be assessed and documented:

- a. Erythema
- b. Edema
- c. Weeping/exudate
- d. Flaking/scaling/dryness

- e. Scabbing/crusting
- f. Erosion/ulceration
- g. Vesiculation/blistering

Per definition, all Local Reactions are causally related to the study treatment.

All Local Reactions will be documented including

- Severity
- Start and stop date

The severity of the local reactions is graded as follows:

Grades	Score	Description
None	0	No signs of reaction
Mild	1	Slight signs of reaction
Moderate	2	Definite signs of reaction
Severe	3	Subject discontinues study product due to reaction

The Investigator will record all adverse events, regardless of relationship to study product, on the adverse event CRF. Standard medical terminology should be used when describing adverse events. Whenever possible a diagnosis should be made and recorded on the CRF rather than listing signs and symptoms. Intermittent adverse events can be recorded once. The anatomical location of the adverse event must be specified, when applicable, as well as whether the location is a treatment area. The following information should be recorded on the CRF:

1. Description
2. Start date
3. Stop date or date of death, ongoing, or unknown
4. Severity of the event (see [8.3.1: Severity](#) for details)
5. Study product use continued or not
6. Outcome of the event (recovered/resolved, recovered/resolved with sequelae, not recovered/not resolved, unknown, fatal)
7. Relationship to study product (see [8.3.2: Relationship to Study Product \(Causality\)](#) for details)
8. Indication of whether the event is serious (see [8.3.3: Seriousness](#) for details)
9. Action taken including treatment with concomitant medication

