### 4.2 Discussion of Design

The study consists of three phases: Screening (up to 60 days), Treatment (12 weeks) and Follow-Up (4 weeks). In Groups 2 and 4, the randomized investigational products will be applied twice daily for 12 weeks to cover the entire single contiguous 5 cm x 5 cm (25 cm^2) lesional area on the face and/or scalp. In Groups 1 and 3, the randomized active DFD-07 (celecoxib) Cream product will be applied only in the evening, while the Vehicle for DFD-07 Cream will be applied in the morning to keep the blinding between groups.

Subjects in all the groups will undergo a further 4-week treatment-free period from Week 12 to Week 16 (End of Study).

The investigational products will be applied twice daily for 12 weeks to cover the entire lesional area (5 cm x 5 cm) on the face and/or scalp identified by the Investigator for treatment. The dose for the study product will be a maximum of 0.5 g per application to the entire 5 cm x 5 cm area on the face and/or scalp for a maximum dose of 1.0 g per day.

Subject visits are scheduled at Screening (Visit 1), Baseline (Visit 2 - Day 1), and Weeks 4 (Visit 3), 8 (Visit 4), 12 (Visit 5) and 16 (Visit 6). Clinical determinations of efficacy will be conducted based on clinically visible or palpable lesions of AK in the treated areas at Weeks 4, 8, 12 and 16 in comparison to Baseline. Comparisons will be made between the different strengths and dosing regimens of DFD-07 (celecoxib) Cream and Vehicle Cream.

Local cutaneous tolerability will be determined at Visits 2 – 6 for the entire treated area. Other safety assessments include physical examinations (HEENT, lungs, heart, abdomen, skin,

---

neurologic), laboratory assessments, electrocardiogram (EKG), vital signs (blood pressure, pulse rate), urine pregnancy tests, and collection of adverse event data.

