2.5.2. Safety and Local Tolerability Evaluation

A safety and local tolerability evaluation will be performed at baseline and each post-baseline visit. This evaluation will include: erythema, edema, weeping/exudate, flaking/scaling/dryness, scabbing/crusting, erosion/ulceration and vesiculation/blistering.

These results will be summarized as frequency and percentages for each evaluation by severity (None, Mild, Moderate and Severe) at each visit in which the evaluation took place.

This information will also be presented in subject data listings.

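### The top grade for local skin reactions records stopping the product, not intensity, so Severe in the descriptive severity table mixes the two

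*Protocol*

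**What the plan says.** Protocol Section 8.2 requires seven kinds of local reaction in the treatment area to be documented separately from adverse events, each with a severity and start and stop dates. Its severity table scores None (0) and Mild (1) by the absence or slightness of signs. Moderate (2) is "Definite signs of reaction" and Severe (3) is "Subject discontinues study product due to reaction".

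Protocol Section 4.2 sets the visits: "Local cutaneous tolerability will be determined at Visits 2 – 6 for the entire treated area". These are Baseline and Weeks 4, 8, 12 and 16, five in all. SAP Section 2.5.2 agrees: "A safety and local tolerability evaluation will be performed at baseline and each post-baseline visit". It then summarises each reaction "by severity (None, Mild, Moderate and Severe) at each visit in which the evaluation took place". The SAP takes over the four labels and does not redefine any of them.

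**The concern.** A severity scale should order one quantity. Here the first three steps order the intensity of signs and the fourth is an action. The top category therefore depends on how willing the subject or investigator is to continue, as well as on the state of the skin.

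The study's single objective is the dose-response relationship of efficacy and safety. Table 14.3.3 is where a reader will compare the severity of local reactions across 1.25% once daily, 2.5% once daily, 2.5% twice daily and Vehicle. If Severe partly reflects stopping behaviour, that table does not answer how intense the reactions were. Intensity above Moderate that was never recorded at the visit cannot be recovered at analysis.

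**Working it through.** The plan states no figure that depends on this scale, so there is nothing to reproduce. The check sets the texts side by side and adds a labelled illustration.

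**1. What the definitions imply.** Moderate is the highest grade defined by signs and has no upper limit.
- Strong signs, subject continues: grade 3 is not met, so the score is Moderate.
- Slight signs, subject stops because of them: grade 3 is met, so the score is Severe.

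**2. Whether another section cures it.** Protocol Section 8.3.1 has an intensity-type definition of Severe, based on effect on activity, but it is for adverse events. Local reactions have their own table. SAP Section 2.5.2 adds no definition.

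**3. Product status at each scored visit.**

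| Visit | Product status | Can grade 3 arise? |
|---|---|---|
| Baseline | None applied yet (Protocol Section 8: "Baseline assessments are made prior to first application") | No |
| Weeks 4 and 8 | On treatment | Only in a subject who stops |
| Week 12 | Treatment ends for everyone | Only in a subject who stops; hard to tell from planned completion |
| Week 16 | Four weeks off product | Not newly, in subjects who completed treatment |

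At 2 of the 5 visits the top grade cannot newly arise in a subject who completes treatment, yet a Severe row is planned for all five.

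**4. What happens to subjects who stop and leave.** Protocol Section 7.6 asks for End of Study evaluations if possible, but the early-withdrawal list in Section 7.10.7 does not name local tolerability. The rule in Section 11.2.1 that assigns early-termination data to a scheduled visit covers efficacy only. SAP Section 2.2 does not impute safety data. Subjects who meet grade 3 may therefore be missing from the by-visit rows.

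**5. Illustration on assumed rates.** Let n = 60 per arm (Protocol Section 11.1), t = the share of subjects with an intense reaction, and q = the share of those who stop because of it. Ignoring slight reactions that lead to stopping, the expected number tabulated as Severe is n × t × q, and n × t × (1 − q) are recorded as Moderate. The values of t and q are assumptions.

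| t | Intense (n × t) | q | Tabulated Severe | Recorded as Moderate |
|---|---|---|---|---|
| 5% | 3 | 10% | 60 × 0.05 × 0.10 = 0.3 | 2.7 |
| 10% | 6 | 10% | 60 × 0.10 × 0.10 = 0.6 | 5.4 |
| 10% | 6 | 50% | 60 × 0.10 × 0.50 = 3.0 | 3.0 |
| 10% | 6 | 100% | 60 × 0.10 × 1.00 = 6.0 | 0 |
| 20% | 12 | 25% | 60 × 0.20 × 0.25 = 3.0 (5%) | 9.0 |
| 20% | 12 | 75% | 60 × 0.20 × 0.75 = 9.0 (15%) | 3.0 |
| 20% | 12 | 100% | 60 × 0.20 × 1.00 = 12.0 | 0 |

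Over t = 5% to 20% and q = 10% to 100%, tabulated Severe runs from 0.3 to 12 subjects per arm. Two arms with the same 20% of intense reactions, but with 25% and 75% of those subjects stopping, would show 5% and 15% Severe. That gap comes from stopping behaviour alone.

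**The case against.** The strongest reply is that grading tolerability by whether the subject could continue is a legitimate choice, and that one rule applies to all four arms of a randomised, double-blind trial. Severe then has the same meaning in each arm: a reaction that led to stopping. That stands, and it makes the count comparable between arms as a count of stopping. It does not make it a measure of intensity, which is how a None-to-Severe table will be read. The 5% versus 15% contrast also needs arms to differ in stopping behaviour at equal intensity, and nothing in the documents says they will.

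Other points that stand:
- A reader might infer that a listed secondary endpoint is compromised. Endpoint 7 counts subjects with any local skin reaction, without severity, so a move between Moderate and Severe, or between Mild and Severe, leaves it unchanged.
- A reader might infer that grade 3 is impossible for everyone at Week 16. A subject who stopped early because of a reaction could still carry that grade; the documents do not say how this is scored.
- An empty Severe cell at Baseline is to be expected and is not in itself a bias. The protocol also says "Per definition, all Local Reactions are causally related to the study treatment", which sits awkwardly with scoring before the first application.
- Saying that every intense reaction in a continuing subject is graded too low only restates the definition. It gives no frequency.

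One point stands only in part. The adverse event form records whether product was continued and whether the event lay in the treatment area. Because local reactions are documented separately, nothing ensures that each one also appears there.

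**Conclusion.** The defect holds as a matter of definition and rests on no assumed rate. Followed exactly, the plan scores a strong reaction in a continuing subject as Moderate, and a slight reaction that ends treatment as Severe. It cannot produce grade 3 at Baseline, or newly at Week 16 in treatment completers. The consequence is limited to the descriptive severity summary, for which no test is planned.

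It is tempting to conclude that the severity tables are biased in a known direction. The documents do not support that. Intense reactions in continuing subjects lower the Severe count, slight reactions that lead to stopping raise it, and no rate is given for either, so the net direction and size between arms cannot be computed. The illustration shows what is possible, not what is expected. The change is worth making because it is cheap and the lost information cannot be rebuilt later, but it does not threaten the trial's main conclusion.

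**What to change.** In Protocol Section 8.2, define grade 3 by the intensity of signs, as a step above Moderate on the same axis as grades 0 to 2. Add a separate yes/no item for whether product was stopped because of the reaction. Section 8.2 already separates these two facts for adverse events, where severity and continued use of product are distinct items.

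In SAP Section 2.5.2, refer to the revised definition and report the new item beside the severity table, so that intensity and stopping can each be read by arm. The two sections should be reconciled together. This changes measurement only and leaves every rule on stopping product as it is.

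The cost is a small change to the case report form and the site training text, with no added procedure. If enrolment has begun, grades collected under the present definition must be flagged, because a Moderate or Severe recorded then does not mean the same as one recorded afterwards.

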## 8.3 Assessment of Adverse Events

### 8.3.1 Severity

It is the Investigator's responsibility to assess the severity of each adverse event. Descriptions of severity are as follows:

1. **Mild**: Awareness of sign or symptom, but easily tolerated. Not likely to interfere with normal activity or require medical attention.
2. **Moderate**: Discomfort enough to cause interference with usual activity. May require medical intervention.
3. **Severe**: Incapacitating such that normal activity is prevented. Likely requires medical intervention and/or close follow-up.

### 8.3.2 Relationship to Study Product (Causality)

It is the Investigator's responsibility to assess the relationship between the study product and the adverse event. The degree of "relatedness" of the adverse event to the study product should be described using the following categories:

1. **Not Related**: The event is clearly due to extraneous causes (e.g., diseases, environment, etc.). Specify if known. Or, the event is most probably produced by other factors such as the subject's clinical state, therapeutic interventions or concomitant therapy and does not follow a known response pattern to the study product.
2. **Possibly Related**: The event is temporally related to study product use, but can be explained by another etiology. Information on the effect of study product withdrawal may be lacking.
3. **Probably Related**: The event is temporally related to study product use and is consistent with known effects of the study product and/or improves upon withdrawal of the study product.
4. **Definitely Related**: The event follows a reasonable temporal sequence from the time of study product administration and/or follows a known response pattern to the study product, and could not have been produced by other factors such as the subject's clinical state, therapeutic intervention or concomitant therapy, and either occurs immediately following study product administration, or improves on stopping the product, or there is a positive reaction at the application site.

### 8.3.3 Seriousness

It is the Investigator's responsibility to determine the "seriousness" of an adverse event. A serious adverse event (SAE) is any adverse event occurring at any dose that results in any of the following outcomes:

1. Death
2. Life-threatening (subject at immediate risk of death)
3. Inpatient hospitalization or prolongation of hospitalization
4. Results in persistent or significant disability/incapacity
5. Results in congenital anomaly/birth defect

Important medical events that may not result in death, are not life-threatening, or do not require hospitalization may be considered an SAE when, based upon appropriate medical judgment, they may jeopardize the subject and may require medical or surgical intervention to prevent one of the outcomes listed above. Examples of such medical events include allergic bronchospasm requiring intensive treatment in an emergency room or at home, blood dyscrasias or convulsions

---

that do not result in inpatient hospitalization, or the development of drug dependency or drug abuse.

